- To evaluate the pharmacokinetics and pharmacodynamics of repeat doses of SAN-300 in patients with active RA
- To evaluate the preliminary efficacy of repeat doses of SAN-300 in patients with active RA
- To evaluate the immunogenicity of repeat doses of SAN-300 in patients with active RA

Study Design:

This is a multicenter, randomized, double-blind, placebo-controlled, multiple ascending dose study to evaluate the safety, pharmacokinetics (PK), pharmacodynamics (PD), preliminary efficacy, and immunogenicity of subcutaneous (SC) administration of SAN-300 in five cohorts of patients with active RA with inadequate response to disease-modifying anti-rheumatic drug(s) (DMARDs). Planned dose cohorts for Study C2013-0302 are as follows:

	Number of Patients to be Dosed				
Cohort	SAN-300	Placebo	SAN-300 Dose		
Α	6	2	0.5 mg/kg SC once weekly		
В	6	2	1.0 mg/kg SC once weekly		
С	6	2	2.0 mg/kg SC every other week		
D	6	2	4.0 mg/kg SC every other week		
E	6	2	4.0 mg/kg SC once weekly		
F	6	2	2.0 mg/kg SC once weekly		

Abbreviations: SC = subcutaneous

Santarus, Inc.
SAN-300 Clinical Trial Protocol: C2013-0302

Amendment 5: 28 Mar 2016

This is a multiple ascending dose study that will enroll patients sequentially into Cohorts A through F. All patients from each cohort will receive a total of 6 weeks of exposure to SAN-300 or placebo at their assigned dose and administration frequency. For the purposes of this protocol, the term "study drug" will include both SAN-300 and placebo.

Safety and tolerability findings will be reviewed in a blinded manner, after each Cohort is fully enrolled and subjects have completed the 6-week Treatment Period (defined as completion of the Week 7 visit) to assess the study drug safety profile and determine whether enrollment will begin in the next cohort. Any subject who withdraws prior to the end of the 6-week Treatment Period will not be replaced and the Study Safety Committee will review the data from all subjects regardless of duration of participation in the study. The safety review will include, at minimum, the following information: adverse events (AEs); safety laboratory results; vital sign measurements; and reasons for premature study withdrawal.

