The decision to begin enrollment in the next cohorts will be based upon the results of the safety review. In addition, based on the findings from the safety review, the Sponsor may elect to modify the dose in the next cohort to a lower dose or terminate any further dose escalation.

Individual patient dosing will be stopped if the patient experiences any of the following: a confirmed reduction in absolute neutrophil count (ANC) to < $1.0 \times 10^3/\mu$ L; a clinically significant atypical or opportunistic infection (including those listed in Appendix 1); or a clinically significant adverse event related to study participation, in the opinion of the investigator. Study enrollment will be temporarily halted if any of the following occur: two or more patients in the study experience a confirmed reduction in ANC to < $1.0 \times 10^3/\mu$ L, any one patient experiences a clinically significant atypical or opportunistic infection (including those listed in Appendix 1), or any other significant safety risk occurs, as noted by the Sponsor. Resumption of study enrollment will be contingent upon further safety review.

All patients will attend a minimum of 10 study visits: one Screening Visit, seven visits during the Treatment Period, and two follow-up visits. Additionally, all enrolled patients will be required to visit the clinic between certain study drug administrations for blood draws for the assessment of PK/PD endpoints. Patients are expected to remain on their existing, background RA regimen for at least the duration of the Follow-up Period. For a more detailed list of individual assessments, refer to the Schedule of Assessments in Appendix 2 and the Specialty PK and PD Laboratory Testing Schedule in Appendix 3.

Screening: Between Days -21 and -1. Informed consent will be obtained before any study specific procedures are performed. Eligibility assessments will be performed.

Treatment Period: Days 1 to 43. Baseline assessments and measurements will be made before dosing with study drug. Patients will receive SC injections of study drug as follows:

- For all cohorts, patients randomized to receive placebo will be administered a total of six once-weekly injections of placebo on Days 1, 8, 15, 22, 29, and 36.
- In Cohorts A, B, E and F, patients randomized to receive SAN-300 will be administered a total of six once-weekly injections of study drug on Days 1, 8, 15, 22, 29, and 36.

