3 INVESTIGATIONAL PLAN

3.1 Overall Study Design and Plan

This is a multicenter, randomized, double-blind, placebo-controlled, multiple ascending dose study to evaluate the safety, tolerability, PK, PD, preliminary efficacy, and immunogenicity of SC administration of SAN-300 in five cohorts of patients with active RA. The study will recruit approximately 40 patients (30 SAN-300; 10 placebo) with active RA to evaluate repeat doses of SAN-300 compared with placebo. The study will be conducted at multiple study centers in the United States.

A study design schematic describing the progression of cohorts in this ascending-dose study is provided in Figure 1. Refer to Section 5.2 for the method of treatment group assignment.

The study will initially enroll patients in Cohort A, in which patients will receive six once-weekly SC administrations of 0.5 mg/kg SAN-300 or placebo. After Cohort A has completed the 6-week Treatment Period (defined as completion of the Week 7 visit), a Study Safety Committee will conduct a blinded Safety Committee Review (including, but not limited to; adverse events (AEs), safety laboratory assessments, vital sign assessments, and reasons for premature study withdrawal) for all patients. If the Study Safety Committee determines that the safety profile is acceptable, then Cohort B can begin enrollment. Subsequent Safety Committee Reviews will take place following each dosing cohort. If the Study Safety Committee determines that the safety profile continues to be acceptable, then enrollment can begin into the next cohort.

Any subject who withdraws prior to the end of the 6-week Treatment Period will not be replaced and the Study Safety Committee will review the data from all subjects regardless of duration of participation in the study.

Based on the findings of the Study Safety Committee, the Sponsor may elect to modify the dose in the next cohort to a lower dose or terminate any further dose escalation.

[figure not shown]
For the purposes of this protocol, the term "study drug" will include both SAN-300 and placebo.

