3.4 Stopping Rules for Individual Patient Dosing and for Study Enrollment

The investigator must notify the Clinical Project Manager immediately (via telephone or email) if a patient experiences any of the events listed in the individual patient dosing or study enrollment stopping rules.

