3.4.2 Stopping Rules for Study Enrollment

New patient enrollment into the study will be temporarily halted, pending review by the Study Safety Committee, under the following circumstances:

• Two or more patients in the study experience a confirmed reduction in ANC to $< 1.0 \times 10^3 / \mu L$.

Amendment 5: 28 Mar 2016

• Any one patient experiences a clinically significant atypical or opportunistic infection (including those listed in Appendix 1).

Any other significant safety risk occurs, as noted by the Sponsor.

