5 TREATMENTS TO BE ADMINISTERED

5.1 Planned Dose Cohorts

Eligible patients will be enrolled into a dose cohort and randomized (3:1) to receive either SAN-300 via SC injection over 6 weeks or a matching volume of placebo. More than one SC injection may be required (maximum volume of 1.2 mL per SC injection) depending on the total dose administered and the weight of the individual patient. Dosing by cohort is provided in Table 2.

Table 2. Dose Cohorts for Study C2013-0302

	Number of Patients to be Dosed		
Cohort	SAN-300	Placebo	SAN-300 Dose
А	6	2	0.5 mg/kg SC once weekly
В	6	2	1.0 mg/kg SC once weekly
С	6	2	2.0 mg/kg SC every other week
D	6	2	4.0 mg/kg SC every other week
Е	6	2	4.0 mg/kg SC once weekly
F	6	2	2.0 mg/kg SC once weekly

Abbreviations: SC = subcutaneous

Safety and tolerability findings will be reviewed in a blinded manner for all patients in a cohort after the 6-week Treatment Period to determine whether or not enrollment will begin in the next cohort. Any subject who withdraws prior to the end of the 6-week Treatment Period will not be replaced and the Study Safety Committee will review the data from all subjects regardless of duration of participation in the study. The safety review will include, at minimum, the following information: AEs; safety laboratory results; vital sign measurements; and reasons for premature study withdrawal.

The decision to begin enrollment in the next cohort will be based upon the results of the safety review. In addition, based on the findings of the Study Safety Committee, the Sponsor may elect to modify the dose in the next cohort to a lower dose or terminate any further dose escalation.

Refer to Section 3.4 for patient and study stopping rules.

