5.2 Method of Assigning Patients to Treatment Groups

Fixed allocation will be used to randomize patients in a ratio of three on SAN-300 to one on placebo within each cohort of approximately 8 total patients.

Cohort A will be enrolled first, with 6 patients randomly assigned to receive SAN-300 and 2 patients randomly assigned to receive matching placebo in two blocks of four patients (three on SAN-300, one on placebo). After Cohort A has completed the 6-week Treatment Period, a Study Safety Committee will conduct a blinded safety review. If the Study Safety Committee determines that the safety profile is acceptable, then Cohort B can begin enrollment. Additional Safety Committee reviews will occur following completion of the 6-week Treatment Period for each of the subsequently enrolled cohorts.

Santarus, Inc.
SAN-300
CONFIDENTIAL
SINCE CONFIDENTIAL
Clinical Trial Protocol: C2013-0302

SAN-300 Amendment 5: 28 Mar 2016

Randomization will be central and occur after a patient has been deemed eligible. Randomization will be performed by Interactive Voice/Web Response System (IVRS/IWRS). The unblinded pharmacist or designated study center personnel assigned to this role will be responsible for obtaining the treatment assigned to each patient in each cohort by contacting the IVRS/IWRS system by phone or Web site. This unblinded person will then prepare the study drug and provide it to the Investigator. The study drug will then be administered by qualified, blinded study personnel on the day of or within 24 hours after randomization.

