7.2 Procedures for Early Withdrawal

When it is determined that a patient should withdraw from the study, the reason(s) must be recorded, final assessments must be scheduled, and provisions for the continued treatment of RA within the standards of care must be discussed with the patient. Safety and study endpoint evaluations for the Early Withdrawal Visit (see Sections 10.2.6 and 10.3.1) will be performed as soon as possible after the decision is made to withdraw the patient.

Additional interventions (concomitant medications or therapies) may be prescribed as needed by the patient. The patient's history and preferences should be considered and discussed when prescribing a new medication for RA.

Appropriate medical follow-up with the patient should be conducted as clinically indicated after the Early Withdrawal Visit. Telephone contacts between the patient and the study staff should be conducted as frequently as needed.

If the patient is found to have an AE or clinically significant laboratory abnormality, the patient will be followed until the event/abnormality is resolved, or until the Investigator determines that further follow-up is no longer medically indicated. The responsible IEC/IRB should be notified of any AEs and/or circumstances leading to early withdrawal.

Amendment 5: 28 Mar 2016

If a patient is withdrawn from study participation because of pregnancy, Product Safety and IEC/IRB should be informed by the site within 24 hours of awareness. All pregnancies occurring in female patients must be reported. The pregnancy will be reported according to the procedures provided in Section 9.8. Should the patient have a spontaneous abortion or complications during the pregnancy, then the event must be captured as an SAE. Sites are obligated to follow the patient until the outcome of the pregnancy is known. The patient and/or her treating physician should be encouraged to report any future medical problems the child develops of which they become aware that are considered related to the study drug.

Patients who are randomized and who subsequently withdraw from the study will not be replaced.

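### Once a cohort is full, a Section 3.4.2 trigger compels no Study Safety Committee review earlier than the one already scheduled after Week 7, because its enrollment halt has nothing to act on and its review has no deadline

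*Protocol*

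**What the plan says.** Section 3.4.2 lists three triggers: two or more patients in the study with a confirmed ANC below 1.0 × 10³/µL, one clinically important atypical or opportunistic infection, or another major safety risk identified by the Sponsor. The consequence is stated as "New patient enrollment into the study will be temporarily halted, pending review by the Study Safety Committee, under the following circumstances". The synopsis has the same rule: "Study enrollment will be temporarily halted if any of the following occur". Section 3.4.3 makes reopening depend on the committee's approval. None of these places gives a time limit, and none holds dosing in patients other than the one affected, who is covered by Section 3.4.1.

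Separately, escalation is gated by cohort. The synopsis times the review "after each Cohort is fully enrolled and subjects have completed the 6-week Treatment Period (defined as completion of the Week 7 visit", that is, Day 43). Section 3.1 adds: "If the Study Safety Committee determines that the safety profile continues to be acceptable, then enrollment can begin into the next cohort". Section 5.1 says the review is held "to determine whether or not enrollment will begin in the next cohort", and Section 5.2 applies it to every cohort: "Additional Safety Committee reviews will occur following completion of the 6-week Treatment Period for each of the subsequently enrolled cohorts". A full cohort cannot reopen, because "Patients who are randomized and who subsequently withdraw from the study will not be replaced" (Section 7.2).

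The surrounding safeguards are these:

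- Section 3.4: "The investigator must notify the Clinical Project Manager immediately (via telephone or email) if a patient experiences any of the events listed" in either set of stopping rules.
- Section 3.5: the committee sees ongoing blinded data, may recommend dosing changes, and judges whether interrupted dosing or enrollment may resume.
- Sections 9 and 9.7: SAEs are reported within 24 hours and reviewed in real time.
- Section 7.3: the Sponsor may end the study at any time.

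**The concern.** The protocol treats these events as serious enough to stop the study taking in patients until its committee has looked at them. That works while a cohort is filling. After the 8th randomization, enrollment is shut anyway and stays shut until the same committee has met. The halt then changes nothing, and the undated review can be satisfied by the meeting already planned.

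The patients exposed in that window are those already enrolled at the same dose. Stopping the affected patient does not stop them, and no text obliges the committee, with its two independent physicians, to consider at the time of the event whether they should go on. Safety and tolerability are the primary objective, and the risks are foreseen: Section 1.3 reports transient ANC reductions in 12 SAN-300 subjects in Phase 1, and Section 1.2.3 reports *Plasmodium* recrudescence in monkeys.

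**Working it through.** The protocol gives no figure for this rule, so there is none to reproduce. The check has two parts.

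**1. What a trigger adds, by period**

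- *Cohort still enrolling:* the halt takes effect, and the committee must meet before the cohort can continue.
- *Cohort full, not the last:* enrollment is already closed. The halt carries over to the next cohort under Section 3.4.3, but the cohort gate already needs the same committee's approval.
- *Last cohort full:* no enrollment remains.
- *Follow-up event while the next cohort is enrolling:* the halt takes effect again.

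The gap is therefore the window from the 8th patient's Day 1 to that patient's Day 43 (43 − 1 = 42 days), plus the time to convene.

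**2. Size of the window**

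Inputs from the protocol are 8 patients per cohort (6 SAN-300, 2 placebo), two blocks of four, weekly injections on Days 1 to 36, and the review after Day 43. Accrual is not stated, so I assume even entry over W weeks, no withdrawals, an event equally likely at any on-treatment time, and nobody acting earlier by discretion.

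Entry times are t_i = (i − 1)W/7 for i = 1 to 8. Each patient is on treatment for 6 weeks, so the total is 48 patient-weeks.

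- Closed share = 1 − Σ min(6, W − t_i)/48.
- On-treatment time in the window for patient i: L_i = 6 − min(6, W − t_i).
- Mean wait to the 8th patient's Day 43 = 6 − ΣL_i²/(2ΣL_i).
- Mean time gained by a 7-day limit = mean of max(wait − 1, 0).

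Worked for W = 8:

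- Σ min(6, 8 − t_i) = 6 + 6 + 5.714 + 4.571 + 3.429 + 2.286 + 1.143 + 0 = 29.143. Closed share = 1 − 29.143/48 = 0.393.
- ΣL_i = 18.857 and ΣL_i² = 82.122. Mean wait = 6 − 82.122/37.714 = 3.82 weeks.
- Only the 8th patient's last week gives a wait under one week: 1/18.857 = 5.3%, so 94.7% wait longer than 7 days.
- Mean gain = 3.8225 − 1 + 0.5/18.857 = 2.849 weeks.

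The injection counts follow from doses at t_i + 0 to 5 weeks. SAN-300-only counts are by simulation over the 3:1 blocks, with the event in a SAN-300 patient.

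| W (weeks) | 4 | 8 | 12 | 24 | 36 |
|---|---|---|---|---|---|
| On-treatment time in closed window | 67% | 39% | 29% | 18% | 14% |
| Mean wait to scheduled review (weeks) | 3.8 | 3.8 | 3.8 | 3.5 | 3.3 |
| Wait longer than 7 days | 95% | 95% | 93% | 88% | 85% |
| Mean gain from a 7-day limit (weeks) | 2.8 | 2.8 | 2.8 | 2.6 | 2.4 |
| Injections left in other 7 patients at event | 11.1 | 5.9 | 3.8 | 1.5 | 0.6 |
| Of these, after day 7 | 6.5 | 3.6 | 2.4 | 1.0 | 0.5 |
| SAN-300 only, after day 7, weekly cohort | 4.7 | 2.5 | 1.6 | 0.7 | 0.3 |
| Same, second ANC case in cohort also stopped | 3.7 | 2.0 | 1.3 | 0.6 | 0.3 |

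In Cohorts C and D (every other week), about half of the SAN-300 figures apply. The two rows of injections in the other 7 patients include placebo. The after-day-7 rows count injections the committee could consider, not injections certain to be averted.

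An extreme case for scale: if all 8 patients were on the same study day and one SAN-300 patient had an infection trigger on Day 8 before dosing, the scheduled review would be 43 − 8 = 35 days away. The 5 other active patients could still receive 5 × 5 = 25 weekly doses, or 5 × 2 = 10 every other week.

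**The case against.** The strongest reply is that Section 3.4.2 does call for a committee review, and nothing says the review lapses or waits for Week 7 when enrollment is closed. Section 3.5 gives the committee ongoing data and lets it recommend dosing changes at any time. It also rules on resuming an individual's dosing after a Section 3.4.1 stop, and the ANC and infection triggers are such stops. A Sponsor representative sits on the committee, and the Sponsor hears of the event at once. This stands in part: the review is undated, not absent, and early action is enabled. But enabling is not requiring. Committee involvement through Section 3.4.1 arises only if resumption is considered for that patient, SAE review belongs to the Sponsor, and a confirmed low ANC need not be an SAE.

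The size can also be challenged. The figures are conditional on a trigger falling in the window, and the documents give no trigger probability. Multiplying the closed share by the SAN-300 injections after day 7 gives, per on-treatment trigger in a weekly cohort, about 3.1, 1.0, 0.5, 0.1 and 0.05 for W = 4 to 36 weeks. Phase 1 was reassuring, though limited to single doses: the ANC reductions were Grade I/II and all resolved, with no severe or serious infections. This too stands, and keeps the point modest. Seven days is a judgement; the documents do not supply a limit.

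A reader might infer that the gap falls hardest on the highest exposure, because SAP Section 3.5 reports 41 randomized and SAP Section 7.1 omits 2.0 mg/kg weekly, which would make Cohort E (24.0 mg/kg overall, Table 1) the last. That is an inference from the SAP, which still tabulates Cohort F as optional. The protocol's planned last cohort is F, at 12.0 mg/kg overall, and E is followed by a gate.

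**Conclusion.** The concern holds in a limited form. In the window between a cohort's last randomization and its post-Week 7 review, including in the last cohort, a Section 3.4.2 trigger compels no committee review earlier than the scheduled one. A reader might go further and conclude that such events go unreviewed or that oversight is missing; the documents do not support that, given Sections 3.4, 3.4.1, 3.5, 7.3 and 9. What is missing is a mandatory date.

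Under the accrual assumptions above, the time gained by a 7-day limit exceeds two weeks at every rate tried. The number of remaining injections it touches depends heavily on accrual and is small if accrual is slow. The conclusion about the rule itself rests on the text alone and does not depend on those assumptions.

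**What to change.** In Section 3.4.2 and the synopsis, add: *Any of these events also requires an ad hoc Study Safety Committee review within 7 days of notification, and where possible before the next weekly dosing visits, whether or not enrollment is open. The committee will recommend to the Sponsor whether patients still receiving study drug should continue dosing.*

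Add a matching line to the committee's duties in Section 3.5. The verb should be *recommend*, since Section 3.5 has the committee recommend dosing modifications and Section 3.1 leaves dose changes to the Sponsor. Leave Section 3.4.3 and the study-wide ANC count as they are.

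An automatic hold on all dosing after a trigger would be a stricter alternative, but it goes beyond what is needed to close this gap.

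The cost is a few sentences and possibly one extra meeting of the existing committee. No patients, visits or staff are added.

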3.4.3 Resumption of Study Enrollment

Resumption of study enrollment will be contingent upon review and approval by the Study Safety Committee.

3.5 Study Safety Committee

The Study Safety Committee will be composed of, at a minimum, a Sponsor representative and two independent expert physicians. This committee will review ongoing blinded study safety data, decide whether dose escalation is appropriate (see Section 3.1 for the role of safety reviews in dose escalation), recommend any modifications in dosing, and evaluate whether resumption of individual patient dosing or study enrollment is permissible after any interruption triggered by the stopping rules for patient dosing and for study enrollment (see Section 3.4).

Santarus, Inc.
SAN-300 Clinical Trial Protocol: C2013-0302

Amendment 5: 28 Mar 2016

4 STUDY POPULATION SELECTION

4.1 Study Population

It is planned that approximately 40 patients (approximately 8 per cohort) with active RA will be enrolled into this study.

